5.6.3 Use in Pregnancy

If a subject inadvertently becomes pregnant while on treatment with lenalidomide-pembrolizumab, the subject will immediately be removed from the study. The site will contact the subject at least monthly and document the subject's status until the pregnancy has been completed or terminated. The outcome of the pregnancy will be reported to the Sponsor and to Merck without delay and within 24 hours to the Sponsor and within 2 working days to

Merck if the outcome is a serious adverse experience (e.g., death, abortion, congenital anomaly, or other disabling or life-threatening complication to the mother or newborn).

The study investigator will make every effort to obtain permission to follow the outcome of the pregnancy and report the condition of the fetus or newborn to the Sponsor. If a male subject impregnates his female partner the study personnel at the site must be informed immediately and the pregnancy reported to the Sponsor and to Merck and followed as described above and in Section 7.2.2.

5.6.4 Use in Nursing Women

It is unknown whether pembrolizumab and lenalidomide are excreted in human milk. Since many drugs are excreted in human milk, and because of the potential for serious adverse reactions in the nursing infant, subjects who are breast-feeding are not eligible for enrollment.

5.7 Subject Withdrawal/Discontinuation Criteria

Subjects may withdraw consent at any time for any reason or be dropped from the trial at the discretion of the investigator should any untoward effect occur. In addition, a subject may be withdrawn by the investigator or the Sponsor if enrollment into the trial is inappropriate, the trial plan is violated, or for administrative and/or other safety reasons. Specific details regarding discontinuation or withdrawal are provided in Section 7.1.4 – Other Procedures.

A subject must be discontinued from the trial for any of the following reasons:

- The subject or legal representative (such as a parent or legal guardian) withdraws consent.
- Confirmed radiographic disease progression

Note: For unconfirmed radiographic disease progression, please see Section 5.2.2

Note: A subject may be granted an exception to continue on treatment with confirmed radiographic progression if clinically stable or clinically improved, please see Section 7.1.2.7.1

- Unacceptable adverse experiences as described in Section 5.2.1.2
- Intercurrent illness that prevents further administration of treatment
- Investigator's decision to withdraw the subject
- The subject has a confirmed positive serum pregnancy test

- Noncompliance with trial treatment or procedure requirements
- The subject is lost to follow-up
- Completed 24 months of uninterrupted treatment with pembrolizumab.
- Administrative reasons

The End of Treatment and Follow-up visit procedures are listed in Section 6 (Protocol Flow Chart) and Section 7.1.5 (Visit Requirements). After the end of treatment, each subject will be followed for 30 days for adverse event monitoring (serious adverse events will be collected for 90 days after the end of treatment as described in Section 7.2.3.1). Subjects who discontinue for reasons other than progressive disease will have post-treatment follow-up for disease status until disease progression, initiating a non-study cancer treatment, withdrawing consent or becoming lost to follow-up. After documented disease progression each subject will be followed by telephone for overall survival until death, withdrawal of consent, or the end of the study, whichever occurs first.

5.7.1 Discontinuation of Study Therapy after CR

Discontinuation of treatment may be considered for subjects who have attained a confirmed CR or after completion of 12 months of therapy.

5.8 Subject Replacement Strategy

If a subject drops out of the study before the first evaluation for reasons different than disease progression or death related to underlying lymphoma or toxicity from the treatment, he or she might be replaced.

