5.3.1.3 Definition of Dose-Limiting Toxicity

Toxicities should be attributable to the study intervention to constitute a dose limiting toxicity (DLT). Toxicity will be graded using the Common Toxicity Criteria for Adverse Events (CTCAE) version 4.0. A DLT is defined by the occurrence of any of the following toxicities (CTCAE v.4.03) for up to 21 days from initiation of the combination therapy (i.e. within the first cycle of therapy) in order to evaluate the potential toxicities of these therapies.

Non-Hematological dose-limiting toxicity

Any Grade 3 or Grade 4 non-hematological toxicity that is possibly, probably or definitely attributable to the regimen pembrolizumab-lenalidomide is considered a DLT, including the following:

- Any type of grade 3-4 hypersensitivity reaction (i.e.: allergic reaction, anaphylaxis, serum sickness, skin disorders, etc.), regardless of attribution.
- Any type of grade 3-4 immune related adverse event
- Inability to receive pembrolizumab-lenalidomide therapy within a 1 month period of scheduled treatment, due to a therapy related event.
- Grade 3 nausea/vomiting/diarrhea lasting longer than 24hours despite maximal care or Grade 4 nausea/vomiting/diarrhea

Any other non-hematologic clinical toxicity considered at least possibly related to treatment defined as any Grade 3 or greater with the specific exception of:

- Grade 3 dehydration that, in the opinion of the investigator, occurs in the setting of inadequate prophylactic measures or compliance with supportive care measures and lasts for less than 48 hours
- Grade 3 fatigue or Grade 4 fatigue that lasts for ≤ 5 days
- Grade 3 fever
- Grade 3 ALT/AST elevation for which total bilirubin remains within normal limits.

Hematologic dose-limiting toxicity

The following hematological toxicity possibly, probably or definitely attributable to the regimen of pembrolizumab and lenalidomide is considered a DLT. Growth factors are allowed per treating investigator's discretion in patients at high risk for febrile neutropenia.

- Grade 4 neutropenia associated with fever (> 38.5) of any duration
- Grade 3 neutropenia associated with fever (> 38.5) of any duration
- Grade 4 thrombocytopenia or Grade 3 thrombocytopenia with bleeding or any requirement for platelet transfusion.
- Grade 4 anemia unexplained by underlying disease
- Myelosuppression that causes a delay of > 7 days in next cycle of pembrolizumab/lenalidomide

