7.0 STATISTICAL ANALYSIS PLAN

7.1 Phase I Statistical Analysis Plan

The primary objective of the Phase I portion of this trial is to identify the MTD (Phase II dose) which is the dose at which the estimated proportion of patients with DLTs is less than 0.33. The standard 3+3 design is employed. Patients will be treated in cohorts of 3 patients starting with Dose Cohort A with lenalidomide 15mg PO day 1-14 and pembrolizumab 200mg IV day 1, in cycles of 21 days, until disease progression or toxicity up to 24 months. The number of patients expected to be enrolled in the dose escalation study is 9 (up to 12 patients if unexpected toxicity is observed).

If 0 out of 3 patients at a particular dose level experiences a dose limiting toxicity (DLT) within Cycle 1 of treatment, if in Dose Cohort A (lenalidomide 15mg) dose escalation will proceed to cohort B (lenalidomide 20mg), if in Dose Cohort B, 3 additional patients will be added. If a DLT occurs in 0 of 6 patients enrolled on Dose Cohort B this will be deemed the Maximum Tolerated Dose (MTD).

If a DLT occurs in only 1 out of 6 patients enrolled at a particular dose level, dose escalation will occur, however, if this occurs on Dose Cohort B (lenalidomide 20 mg) or Dose Cohort Z (lenalidomide 10 mg), this will be deemed the Maximum Tolerated Dose (MTD). MTD is defined as the highest dose level at which < 33% of 6 patients experience a DLT.

If a DLT occurs in ≥ 2 of 3 patients or ≥ 2 of 6 patients treated on Dose Cohort A (lenalidomide 15mg), there will be a dose de-escalation to Dose Cohort Z (lenalidomide 10 mg).

If a DLT occurs in ≥ 2 of 3 patients or ≥ 2 of 6 patients treated on Dose Cohort B (lenalidomide 20 mg) or the preceding dose level will be declared the MTD if there were no more than 1 DLT in this previous cohort.

If a DLT occurs in ≥ 2 of 3 patients or ≥ 2 of 6 patients on Dose Cohort Z (lenalidomide 10mg), the trial will be discontinued and the expanded cohort will not be implemented.

Once the MTD has been determined, 17 additional patients with relapsed refractory HL will be treated in in the Phase II portion of this trial at the MTD.

While clinical benefit rates and other outcome rates for each dose cohort will be estimated, all of the summary of patient outcomes is descriptive.

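### Section 5.8 makes no provision for replacing Phase 1 patients lost in cycle 1 to progression or lymphoma death, and the 3+3 counts do not require DLT-evaluable patients

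*Combined protocol and SAP*

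**What the plan says.** Section 5.8 is the only replacement rule, and it does not distinguish the phases. It opens with "If a subject drops out of the study before the first evaluation" and allows replacement "for reasons different than disease progression or death related to underlying lymphoma or toxicity from the treatment, he or she might be replaced". The first evaluation is not defined. Cycle 1 falls inside it whether it means the end of the DLT window or the first 12-week imaging.

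Section 5.3.1.3 counts DLTs "for up to 21 days from initiation of the combination therapy (i.e. within the first cycle of therapy").

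The decision rules in 7.1, repeated in 2.1, use varying denominators:
- first step: "If 0 out of 3 patients at a particular dose level experiences a dose limiting toxicity (DLT) within Cycle 1 of treatment";
- second step: "If a DLT occurs in 0 of 6 patients enrolled on Dose Cohort B this will be deemed the Maximum Tolerated Dose (MTD");
- definition: "MTD is defined as the highest dose level at which < 33% of 6 patients experience a DLT".

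Other rules in the same sections refer to patients treated. No section defines a DLT-evaluable patient, sets a minimum cycle 1 exposure, or says how to count a patient who leaves before day 21 without a DLT. Response does have such a condition: section 6.2.2.6 measures it in patients who complete one cycle.

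**The concern.** The 5.8 rule suits a Phase 2 response endpoint, where early progression is itself an outcome and replacing the patient would bias the result. Phase 1 asks a different question. A patient who stops in week 2 because the lymphoma progressed has had only part of a cycle of the combination and may tell us little about its toxicity. Section 5.8 does not provide for replacing that patient, and even for the reasons it does cover, replacement is only optional.

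If the patient nevertheless fills one of the 3 or 6 places without a DLT, the cohort looks complete but holds less safety information than the 3+3 rule assumes. The resulting error favors passing the dose. At stake are the decision to escalate and the choice of the dose carried into Phase 2.

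**Working it through.** **Inputs.** DLT window of 21 days (5.3.1.3); decisions on 3 and 6 patients, with at most 1 DLT in 6 to pass (2.1, 7.1). Expansion to 6 after 1 DLT in 3 is taken from the standard 3+3 design that 7.1 names. True DLT risks *p* of one third (close to the plan's 0.33 limit) and 0.40 are illustrative. The cycle 1 loss rate *q* is not in the documents; 2%, 5% and 10% are assumptions.

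**The plan's own figure.** Section 7.1 states: "The number of patients expected to be enrolled in the dose escalation study is 9 (up to 12 patients if unexpected toxicity is observed"). Three in Cohort A plus six in Cohort B gives 3 + 6 = 9. Six in A plus six in B, or six in A plus six in Z, gives 6 + 6 = 12. Both figures reproduce, and neither leaves room for a replacement.

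**Full cohort.** Once Cohort B is opened, it is declared the MTD with at most 1 DLT in 6:
P6(p) = (1−p)^6 + 6p(1−p)^5.
- p = 1/3: 64/729 + 192/729 = 256/729 = 0.351.
- p = 0.40: 0.0467 + 0.1866 = 0.233.

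**One of the first 3 gives no DLT information, is counted and is not replaced.** The decision now rests on at most 1 DLT in 5:
P5(p) = (1−p)^5 + 5p(1−p)^4.
- p = 1/3: 32/243 + 80/243 = 112/243 = 0.461.
- p = 0.40: 0.0778 + 0.2592 = 0.337.

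**First step alone.** The chance of no DLT is (1−p)^n.
- p = 1/3: (2/3)^3 = 0.296 with 3 informative patients; (2/3)^2 = 0.444 with 2.
- p = 0.40: 0.216 with 3; 0.360 with 2.

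After a clean first step, the exact one-sided 95% upper limit for the DLT rate is 1 − 0.05^(1/n): 63.2% for 0 of 3 and 77.6% for 0 of 2.

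**Does the MTD threshold catch a short cohort?** Section 7.1 asks for "the dose at which the estimated proportion of patients with DLTs is less than 0.33". One DLT in 5 informative patients is 20%, and one in 4 is 25%. Both pass, so it does not.

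**Without conditioning on a loss.** Suppose each of the 6 patients is lost with probability *q*, independently of toxicity, gives no DLT information and is counted as having none. The chance of a recorded DLT per patient is then p(1−q), and the chance of declaring Cohort B the MTD is P6(p(1−q)). At p = 1/3:

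| Assumed q | p(1−q) | P(Cohort B declared MTD) | Rise from 0.351 | At least one loss in 3, 1−(1−q)^3 | At least one loss in 9, 1−(1−q)^9 |
|---|---|---|---|---|---|
| 2% | 0.327 | 0.364 | 0.013 | 5.9% | 16.6% |
| 5% | 0.317 | 0.385 | 0.034 | 14.3% | 37.0% |
| 10% | 0.300 | 0.420 | 0.069 | 27.1% | 61.3% |

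**The case against.** Four points on the other side carry weight.

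1. **Section 5.8 contains no prohibition.** A reader might infer that progressors are expressly irreplaceable. The sentence only says when a subject may be replaced; progression and lymphoma death lie outside that permission by implication. This stands, but it does not supply a rule.

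2. **Stopping treatment does not end observation.** The DLT window runs from the start of therapy. Sections 5.7 and 6.3 provide for adverse event collection for 30 days after treatment ends, and 6.2.4.3 requires a safety visit. A patient who stops on day 12 for progression would normally still be under adverse event collection on day 21. It would therefore be wrong to say that every such patient is unobserved. Usually what is lost is exposure; observation itself is cut short mainly by death, new anti-cancer therapy or loss of contact. The point is partial, because follow-up does not restore a full cycle of treatment. Two DLT criteria in 5.3.1.3, delay of the next cycle and inability to receive therapy, also depend on later dosing that such a patient will not have.

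3. **No text says the patient counts as DLT-free.** That is the natural reading where 7.1 refers to patients enrolled, but 7.1 also refers to patients treated. Section 8.1 adds a safety committee review on a complete cohort data set. Complete is not defined there, so the review is a checkpoint without a criterion.

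4. **Early losses may be rare.** Entry requires ECOG 0 to 1, imaging is every 12 weeks, and the listed trigger is confirmed radiographic progression. Against that, Phase 1 takes relapsed or refractory disease with any number of prior lines, and clinical progression or lymphoma death in cycle 1 remains possible. The documents do not settle the rate.

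**Conclusion.** The point holds as a gap with a predictable direction. One replacement rule serves two phases with different needs, DLT evaluability is undefined, and a short cohort can clear a dose under the rules as written.

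The move from 0.35 to 0.46 (or from 0.23 to 0.34 at 40%) applies only if one of the first 3 patients in Cohort B gives no DLT information, is not replaced and is counted without a DLT. A reader might take this rise of 11 percentage points as the overall effect on the design. The documents do not support that, because they give no loss rate. Under assumed losses of 2% to 10% per patient, the overall rise at one third is about 1 to 7 percentage points, and smaller where follow-up through day 21 recovers the information. The calculation also assumes that loss is independent of toxicity.

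The change should be made: it is cheap, it concerns the Phase 1 primary endpoint, and leaving it open means deciding how to count a patient after the cohort's data are known.

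**What to change.** For Phase 1 only, in sections 2.1, 5.8 and 7.1:

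- **Define DLT-evaluable.** A patient is evaluable if a DLT occurred, or if the patient was followed for DLT through day 21 and met an exposure criterion that the sponsor states in advance.
- **Replace the non-evaluable.** A patient without a DLT who is not evaluable for a reason other than treatment toxicity is replaced. This includes progression and lymphoma death.
- **Keep toxicity exits in the count.** A patient who leaves for treatment toxicity is not replaced, even if the event falls short of a DLT. A rule that replaced every early leaver whatever the reason would remove these patients and could make a dose look safer than it is.
- **State the denominators.** The 3, the 6 and the total of 9 to 12 refer to DLT-evaluable patients. The enrollment totals in 1.0 and 5.2 should be worded to match.

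Keep the existing 5.8 rule for Phase 2.

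The cost is a few sentences of protocol text and possibly one or two more Phase 1 patients if early losses occur.

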5.9 Clinical Criteria for Early Trial Termination

Early trial termination will be the result of the criteria specified below:

1. Quality or quantity of data recording is inaccurate or incomplete
2. Poor adherence to protocol and regulatory requirements
3. Incidence or severity of adverse drug reaction in this or other studies indicates a potential health hazard to subjects
4. Plans to modify or discontinue the development of the study drug

In the event of Merck decision to no longer supply study drug, ample notification will be provided so that appropriate adjustments to subject treatment can be made.

Product: Pembrolizumab and Lenalidomide
Protocol/Amendment No.: Version 3.1 July 18th, 2017

Trial Period:			Treatment Cycles ^a									End of Treatment	Post-Treatment			
			Screening (Visit 1)	Cycle 1 day 1	Cycle 1 day 8	Cycle 1 day 15	2	3	4	To be repeated beyond 8 cycles				Discon	Safety Follow-up	Follow Up Visits
5	6	7								8						
Scheduling Window (Days):	-28 to -1					± 3	± 3	± 3	± 3	± 3	± 3	± 3	At time of Discon	30 days post discon	Every 12 weeks	Every 12 weeks
Directed Physical Examination																
Vital Signs and Weight	X	X	X	X	X	X	X	X	X	X	X	X	X		X	X
Height	X															
ECOG Performance Status	X	X	X	X	X	X	X	X	X	X	X	X	X			
Pregnancy Test – Urine or Serum -HCG ^c	X	X			X	X	X	X	X	X	X	X	X			
PT/INR and aPTT	X	X						X								
Complete Blood Count with Differential	X	X	X	X	X	X	X	X	X	X	X	X	X		X	
Comprehensive Serum Chemistry Panel	X	X	X	X	X	X	X	X	X	X	X	X	X		X	
ESR	X				X	X	X	X	X	X	X	X	X		X	
Urinalysis	X	X			X	X	X	X	X	X	X	X	X		X	
T3, FT4 and TSH	X	X			X	X	X	X	X	X	X	X	X		X	
Tumor Imaging	X							X ^A					X		X	

Product: Pembrolizumab and Lenalidomide
Protocol/Amendment No.: Version 3.1 July 18th, 2017

Trial Period:			Treatment Cycles ^a										End of Treatment	Post-Treatment		
Treatment Cycle/Title:		Screening (Visit 1)	Cycle 1 day 1	Cycle 1 day 8	Cycle 1 day 15	2	3	4	To be repeated beyond 8 cycles				Discon	Safety Follow-up	Follow Up Visits	Survival Follow-Up
Scheduling Window (Days):		-28 to -1				± 3	± 3	± 3	± 3	± 3	± 3	± 3				
Archival or Newly Obtained Tissue Collection		X				X ^b							X			
Correlative Studies Blood Collection		X				X			X				X			
		^a Every week +/- 3 days; except Cycle 1 ^b Day 1 of 21 day cycle ^c Day 1-14 of 21 day cycle ^Λ Every 12 weeks +/- 1 week ^β Biopsy while on therapy is optional ^c For women of child bearing potential: Pregnancy test is required 10-14 days prior to first dose of study drug AND a second pregnancy test is required within 24 hours before first dose of study drug														

Product: Pembrolizumab and Lenalidomide
Protocol/Amendment No.: Version 3.1 July 18th, 2017

TRIAL PROCEDURES

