5.1.3 Subject Exclusion Criteria

The subject must be excluded from participating in the trial if the subject:

1. Is currently participating and receiving study therapy or has participated in a study of an investigational agent and received study therapy or used an investigational device within 4 weeks of the first dose of treatment.
2. Has a diagnosis of immunodeficiency or is receiving systemic steroid therapy or any other form of immunosuppressive therapy within 7 days prior to the first dose of trial treatment.

3. Has a known history of active TB (Bacillus Tuberculosis)
4. Hypersensitivity to pembrolizumab or any of its excipients.
5. Has had a prior anti-cancer monoclonal antibody (mAb) within 4 weeks prior to study Day 1 or who has not recovered (i.e., \leq Grade 1 or at baseline) from adverse events due to agents administered more than 4 weeks earlier.
6. Has had prior chemotherapy, targeted small molecule therapy, or radiation therapy within 2 weeks prior to study Day 1 or who has not recovered (i.e., \leq Grade 1 or at baseline) from adverse events due to a previously administered agent.
 - Note: Subjects with \leq Grade 2 neuropathy are an exception to this criterion and may qualify for the study.
 - Note: If subject received major surgery, they must have recovered adequately from the toxicity and/or complications from the intervention prior to starting therapy.
7. Has a known additional malignancy that is progressing or requires active treatment. Exceptions include basal cell carcinoma of the skin or squamous cell carcinoma of the skin that has undergone potentially curative therapy or in situ cervical cancer.
8. Has known active central nervous system (CNS) metastases and/or carcinomatous meningitis. Subjects with previously treated brain metastases may participate provided they are stable (without evidence of progression by imaging for at least four weeks prior to the first dose of trial treatment and any neurologic symptoms have returned to baseline), have no evidence of new or enlarging brain metastases, and are not using steroids for at least 7 days prior to trial treatment. This exception does not include carcinomatous meningitis which is excluded regardless of clinical stability.

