6.2.2.7 Tumor Tissue Collection and Correlative Studies Blood Sampling

- a) Samples of peripheral blood will be collected pretreatment, at initial staging and at the end of the study in all patients. On these samples flow cytometry, and other immune analysis will be performed to characterize the peripheral blood mononuclear cells populations and their variation as a function of the therapy, and to evaluate circulating immune subsets in patients as a function of treatment.
- b) Immunohistochemistry evaluation of the tumor microenvironment will be performed on patient's initial biopsy. Optional core needle biopsy early during therapy and in relapsing patients at the time of relapse will be submitted for analysis and comparison
- c) Gene expression profiling of the above samples will be concurrently analyzed in collaboration with [name] at BCC Cancer Center.

Product: Pembrolizumab and Lenalidomide
Protocol/Amendment No.: Version 3.1 July 18th, 2017

- d) Evaluation of PD-1 expression in tumor tissue will be performed in collaboration with Merck.

Tissue and blood storage

All blood and tissue samples will be processed immediately and stored indefinitely for later analysis in a locked -80°C freezer in the NYU Biorepository Core for research purposes only. No germline genetic testing will be performed on any specimens collected during this trial. Subjects will not receive the results of any testing.

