7.3 Correlative Studies Statistical Analysis Plan

For each of the correlative studies, summary statistics and graphical displays will be provided over time, changes from baseline will be summarized similarly over time, and baseline levels and changes from baseline will be displayed by response over time.

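### The only pre-treatment immune-profiling blood sample is scheduled at Screening, before the washouts are complete, so the exploratory change from baseline can mix recovery from prior therapy with a study-drug effect

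*Combined protocol and SAP*

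**What the plan says.** **Sampling.** The Trial Flow Chart (Section 6.0) marks "Correlative Studies Blood Collection" under Screening, Cycle 2, Cycle 5 and discontinuation. The three Cycle 1 columns are blank in that row, and the Screening column runs from day -28 to day -1. Section 6.2.2.7 gives no day for the first sample: "Samples of peripheral blood will be collected pretreatment, at initial staging and at the end of the study in all patients".

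**Washouts (Section 5.1.3).** Each is anchored to the start of treatment:
- Item 1, investigational agents or devices: "received study therapy or used an investigational device within 4 weeks of the first dose of treatment".
- Item 2, steroids and immunosuppression: "is receiving systemic steroid therapy or any other form of immunosuppressive therapy within 7 days prior to the first dose of trial treatment".
- Item 5, antibodies: "Has had a prior anti-cancer monoclonal antibody (mAb) within 4 weeks prior to study Day 1".
- Item 6, chemotherapy, small molecules and radiation: "Has had prior chemotherapy, targeted small molecule therapy, or radiation therapy within 2 weeks prior to study Day 1".

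**Analysis.** Section 7.3 states that "changes from baseline will be summarized similarly over time" and that levels and changes will also be displayed by response. It does not say which sample is the baseline.

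**Passages that limit the gap.** Section 5.4.2 bars anticancer therapy and most systemic glucocorticoids during Screening. Section 6.2.3 asks for screening laboratory tests within 10 days before first dose, and its Table 6 lists the correlative blood. Section 5.1.2, item 6, allows 14 days for screening labs. Section 6.2.4.1.1 allows a screening period of up to 30 days.

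**The concern.** The first exploratory hypothesis (Section 3.3) is that chronic activation and exhaustion of circulating immune cells are reversed with treatment in responding patients. The evidence for it will be the change from the pre-treatment sample, displayed by response.

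Chemotherapy, steroids and antibodies can themselves alter circulating immune cells. If the baseline tube is drawn soon after such therapy ends, part of the later change may be recovery that would have occurred without the study drugs. There is no control arm in which to see that recovery, and Section 7.3 plans no account of time since prior therapy.

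What is at stake is how the immune-profiling results are read. A pre-dose sample that was not taken cannot be obtained afterwards.

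**Working it through.** The plan states no figure on this point, so the check is a comparison of dates.

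**Inputs.** Washouts w from Section 5.1.3: 14 days (chemotherapy, small molecules, radiation), 28 days (antibody, investigational agent), 7 days (steroids, immunosuppression). Cycle length is 21 days (Section 2.1). Let d be the number of days from the draw to Day 1: at most 28 (flow chart), 14 (Section 5.1.2) or 10 (Section 6.2.3), and at least 1 for any Screening draw.

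**Formulas.** The shortest gap from last prior therapy to the draw, on the washout alone, is w − d. The drug-free share of the interval from baseline to Cycle 2 Day 1 is d/(d + 21).

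| Draw, days before Day 1 | Chemotherapy, small molecule, radiation | Antibody, investigational agent | Steroid, immunosuppression | Drug-free share |
|---|---|---|---|---|
| 28 (flow chart) | 14 − 28 = −14 | 28 − 28 = 0 | 7 − 28 = −21 | 28/49 = 57% |
| 14 (Section 5.1.2) | 14 − 14 = 0 | 28 − 14 = 14 | 7 − 14 = −7 | 14/35 = 40% |
| 10 (Section 6.2.3) | 14 − 10 = 4 | 28 − 10 = 18 | 7 − 10 = −3 | 10/31 = 32% |
| 1 (latest Screening day) | 14 − 1 = 13 | 28 − 1 = 27 | 7 − 1 = 6 | 1/22 = 5% |
| 0 (Cycle 1 Day 1, pre-dose) | 14 | 28 | 7 | 0% |

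**Effect of Section 5.4.2.** A negative gap would mean that the draw precedes the last prior dose. For the therapies it covers, the bar during Screening largely rules that out. It does not ensure any interval before the draw, because Screening begins at consent (Section 6.2.4.1.1) and the tube can be taken at once. Zero and negative entries therefore become a gap of about 1 day.

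**Under the flow-chart window.** About 1 day is possible for all three groups. For example: last chemotherapy on day -15, consent and draw on day -14, first dose on Day 1. The 14-day rule also permits this.

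**Under the 10-day rule.** That example is excluded. A draw is still permitted about 4 days after chemotherapy and 18 days after antibody. For steroids about 1 day remains possible: last dose on day -8, consent and draw on day -7, first dose on Day 1.

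**Sensitivity.** With the Cycle 2 window of ±3 days, the 57% ranges from 28/52 = 54% to 28/46 = 61%. To Cycle 5 Day 1, 84 days after Day 1, the drug-free share is 28/112 = 25% for a day -28 draw and 10/94 = 11% for a day -10 draw.

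**The case against.** The strongest reply is that the 10-day rule in Section 6.2.3 governs this tube, since Table 6 of that section lists it. If so, the day -14 example is not permitted, and a reader who inferred that the sample may be drawn the day after chemotherapy or antibody under every rule would be wrong. This stands as a limit, and it is why both readings are shown above. It does not close the gap: about 4 days after chemotherapy and 1 day after steroids remain possible, and nothing in the documents says which of the four windows applies to the correlative blood.

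There are other safeguards. Section 5.1.3 requires recovery from adverse events of prior agents to Grade 1 or baseline, and Table 1 sets minimum neutrophil and platelet counts. These limit gross marrow suppression, but they do not standardise immune subsets at the draw. Sections 6.2.1.4.1 and 6.2.1.5.2 have prior medication and cancer treatment recorded, so the gap could be derived if draw dates are kept. That would allow flagging, but Section 7.3 does not plan it and it cannot replace a missing pre-dose sample.

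A site may also draw late in Screening, and a tube taken near day -1 largely avoids the problem. That is true but not required.

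Finally, the endpoint is exploratory, and Section 7.3 attaches no test, threshold or decision to it. This stands, and it sets the weight of the point.

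**Conclusion.** The concern holds as a scheduling weakness in an exploratory analysis. The baseline tube may be drawn before the washouts are complete under every window in the documents, with up to 57% (flow chart) or 32% (10-day rule) of the interval to Cycle 2 Day 1 free of study drug. This rests on the column positions in the flow chart, which should be confirmed against the chart itself, and on the draw being permitted any day after consent within the window that applies.

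Two stronger readings are not supported. A reader might infer that the change from baseline measures recovery in place of a drug effect. The documents show only that the two can be mixed, to a degree that varies with the draw date. A reader might also wish to attach a percentage to the spurious change, or to suppose that it differs between responders and non-responders. The documents give neither the share of patients likely to be sampled early nor the degree of immune suppression at that time, so neither can be worked out. The day counts show opportunity for bias, not its size.

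The MTD, complete response, safety and PFS analyses are unaffected. The change is worth making because it costs little.

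**What to change.** 1. In the Trial Flow Chart, move the baseline correlative blood mark from Screening to Cycle 1 Day 1 and specify pre-dose.
2. In Sections 6.2.2.7 and 7.3, name that sample as the baseline for all change-from-baseline summaries.
3. If a Screening tube is kept as back-up, use it only when the Cycle 1 Day 1 tube is missing and flag it in the summaries. State which of the 10-, 14-, 28- and 30-day windows applies to it.

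**Cost.** Blood count and chemistry are already marked at Cycle 1 Day 1, so no extra visit is needed. Section 5.3.2 already places the flow-chart procedures before dosing on Day 1. The small downside is that a missed pre-dose tube cannot be redrawn, which is the reason to consider a back-up.

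**Limit.** A Day 1 draw guarantees the full 7, 14 or 28 days before baseline. It reduces, but does not remove, carry-over that outlasts the washout.
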